### 3.3 SELECTION OF TRIAL POPULATION

This trial will recruit approximately up to 24 patients in total. The SRD part is expected to enrol 18 patients; the actual number may increase depending on the occurrence of DLEs; please refer to [Section 7.5](#) and [Appendix 10.4](#) for details and justification. The MD part is expected to enrol 6 patients.

Screening of patients for this trial is competitive, i.e. screening for the trial will stop at all sites at the same time once a sufficient number of patients has been screened. Investigators will be notified about screening completion and will then not be allowed to screen additional patients for this trial.

A log of all patients enrolled into the trial (i.e. who have signed informed consent) will be maintained in the Investigator Site File (ISF) irrespective of whether they have been treated with investigational drug or not.

If a patient is entered in error (does not meet all inclusion criteria or meets one or more exclusion criteria on the day of enrolment), the sponsor has to be contacted immediately.

#### 3.3.1 Main diagnosis for trial entry

This trial enrolls patients with GA secondary to AMD as diagnosed by FAF and with significant visual loss selected based on BCVA.

Please refer to [Section 8.3.1](#) (Source Documents) for the documentation requirements pertaining to the in- and exclusion criteria.

#### 3.3.2 Inclusion criteria

1. Men and women with GA secondary to AMD: For the SRD part, the GA lesion in the study eye must be  $\geq 1.9 \text{ mm}^2$  disc area in size (approximately  $\geq 0.75$  disc area in size); for the MD part the total GA lesion size in the study eye must be  $\geq 7.5 \text{ mm}^2$  (approximately  $\geq 3$  disc area in size).
2. Fellow eye is not required to have GA
3. BCVA:
  - a. SRD part: BCVA of 20/100 to 20/400 Snellen (corresponding to 19 to 53 letters in the ETDRS chart) in the study eye equivalent measured by the Early Treatment Diabetic Retinopathy Study (ETDRS) protocol
  - b. MD part: BCVA score of  $\leq 53$  letters (Snellen equivalent of 20/100) in the study eye
4. Age  $\geq$  than 50 years
5. Best-corrected VA in the non-study eye must have a better best-corrected VA compared to the study-eye
6. Women of childbearing potential (WOCBP) cannot be included. Men able to father a child must be ready and able to use highly effective methods of birth control per ICH M3 (R2) that result in a low failure rate of less than 1% per year when used consistently and correctly. A list of contraception methods meeting these criteria is provided in the patient information in [Section 4.2.2.3](#)

Proprietary confidential information © 2022 Boehringer Ingelheim International GmbH or one or more of its affiliated companies

7. Signed informed consent consistent with ICH GCP guidelines and local legislation prior to participation in the trial, which includes medication washout and restrictions
8. Not under any administrative or legal supervision or under institutionalization due to regulatory or juridical order

(1) A woman is considered of childbearing potential (WOCBP), i.e. fertile, following menarche and until becoming postmenopausal unless permanently sterile. Permanent sterilisation methods include hysterectomy, bilateral salpingectomy and bilateral oophorectomy. Tubal ligation is NOT a method of permanent sterilisation. A postmenopausal state is defined as no menses for 2 years without an alternative medical cause. A high follicle stimulating hormone (FSH) level in the postmenopausal range may be used to confirm a post-menopausal state in women not using hormonal contraception or hormonal replacement therapy. However in the absence of 2 years of amenorrhea, a single FSH measurement is insufficient.

### **3.3.3 Exclusion criteria**

1. GA in either eye because of causes other than AMD
2. History of choroidal neovascularization (CNV) in the study eye and in the fellow eye
3. Previous treatment in the study eye for GA secondary to AMD within 6 months prior to screening visit (ongoing therapy with vitamin and mineral supplements is allowed)
4. Previous participation in other trials for treatment of GA receiving active drug in the study eye. For the MD part any patients that participated in SRD part of the trial (regardless of the eye).
5. Additional eye disease in the study eye that could compromise
  - best corrected VA (BCVA) with visual field loss,
  - uncontrolled glaucoma intraocular pressure (IOP>24),
  - clinically significant diabetic maculopathy,
  - history of ischemic optic neuropathy or retinal vascular occlusion,
  - symptomatic vitreomacular traction,
  - genetic disorders such as retinitis pigmentosa);
  - history of high myopia > 8 diopters in the study eye and
  - anterior segment and vitreous abnormalities in the study eye that would preclude adequate observation with SD-OCT
6. Any prior intraocular surgery in the study eye other than uneventful lens replacement for cataract within 3 months prior to screening
7. Aphakia or total absence of the posterior capsule. Yttrium aluminium granat (YAG) laser capsulotomy permitted, more than 3 months prior to enrolment in the study eye
8. Current or planned use of medications known to be toxic to the retina, lens or optic nerve (e.g. desferoxamine, chloroquine/hydrochloroquine, chlorpromazine, phenothiazines, tamoxifen, nicotinic acid, and ethambutol)
9. Significant disease or other medical conditions (as determined by medical history, examination and clinical investigations at screening) that may, in the opinion of the investigator result in any of the following:
  - Put the patient at risk because of participation in the study
  - Influence the results of the study,
  - Cause concern regarding the patient's ability to participate in the study, e.g. cardiac (including tachycardia), gastro-intestinal, hepatic, renal, metabolic, dermatologic, neurological, haematological, oncological and psychiatric.

10. Patients with malignancy for which the patient has undergone resection, radiation or chemotherapy within past 5 years. Patients with treated basal cell carcinoma or fully cured squamous cell carcinoma are allowed.
11. Known hypersensitivity to any of the ingredients used in the IMP formulation, or any of the medications used
12. Active intraocular inflammation in the study eye
13. Active infectious conjunctivitis in either eye
14. For the MD part: Unstable cardiovascular/metabolic disease (e.g. hypertension, diabetes mellitus, hypercholesterolemia) and/or not on stable medication for these conditions at least 3 months prior to inclusion
15. For the MD part: Any evidence for current or past giant cell arteritis

### **3.3.4      Withdrawal of patients from treatment or assessments**

Patients may be withdrawn from trial treatment or withdraw consent to trial participation as a whole (“withdrawal of consent”) with very different implications; please see [Sections 3.3.4.1](#) and [3.3.4.2](#) below.

Every effort should be made to keep the patients in the trial: if possible on treatment, or at least to collect important trial data.

Measures to control the withdrawal rate include careful patient selection, appropriate explanation of the trial requirements and procedures prior to trial enrolment, as well as the explanation of the consequences of withdrawal.

The decision to discontinue trial treatment or withdraw consent to trial participation and the reason must be documented in the patient files and Case Report Form (CRF).

#### **3.3.4.1    Withdrawal from trial treatment**

An individual patient is to be withdrawn from trial treatment if:

- The patient wants to discontinue trial treatment, without the need to justify the decision.
- The patient has repeatedly shown to be non-compliant with important trial procedures and, in the opinion of both, the investigator and sponsor representative, is not willing or able to adhere to the trial requirements in the future.
- The patient needs to take concomitant medication that interferes with the investigational medicinal product or other trial treatment
- The patient can no longer receive trial treatment for medical reasons (such as surgery, adverse events, other diseases, or pregnancy). An AE or clinically significant laboratory change or abnormality occurred that the investigator judges to warrant discontinuation of treatment.

Even if the patient is withdrawn from trial treatment, the patient remains in the trial and, given his/her agreement, will undergo the procedures for early treatment discontinuation and follow-up as outlined in the [Flow Chart I](#) and [Flow Chart II](#) and [Section 6.2](#).

### **3.3.4.2 Withdrawal of consent to trial participation**

Patients may withdraw their consent to trial participation at any time without the need to justify the decision.

This will however mean that no further information may be collected for the purpose of the trial and negative implications for the scientific value may be the consequence. Furthermore, it may mean that further patient follow up on safety cannot occur.

If a patient wants to withdraw consent, the investigator should be involved in the discussion with the patient and explain the difference between trial treatment discontinuation and withdrawal of consent to trial participation, as well as explain the options for continued follow-up after trial treatment discontinuation, please see [Section 3.3.4.1](#) above.

### **3.3.4.3 Discontinuation of the trial by the sponsor**

Boehringer Ingelheim reserves the right to discontinue the trial overall or at a particular trial site at any time for the following reasons:

1. Failure to meet expected enrolment goals overall or at a particular trial site.
2. Emergence of any efficacy/safety information invalidating the earlier positive benefit-risk-assessment that could significantly affect the continuation of the trial.
3. Deviations from GCP, the trial protocol, or the contract impairing the appropriate conduct of the trial.

For the following scenario further enrolment and entering into the trial will be interrupted by the sponsor once the sponsor becomes aware (i.e. stopping rule):

- A single serious adverse reaction (i.e. a single serious adverse event) or two severe adverse reactions in two different patients (regardless of the system organ class) confirmed by both the investigator and sponsor as having a reasonable causal relationship to the IMP administration.
- For the MD part: Occurrence of AION or relevant predisposing changes of the optic disc in the study eye after administration of BI 754132.

The investigator / the trial site will be reimbursed for reasonable expenses incurred in case of trial termination (except in case of the third reason).

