### 1.4.3 Discussion

Considering the data available from previous non-BI clinical trials evaluating the same MoA (see [Section 1.4.2.1](#)), and data from pre-clinical studies on BI 754132, in this trial extensive ophthalmic and systemic examinations are planned in all the visits.

Blood tests and physical examination will evaluate potential changes in blood cell count and fibrinogen plasma levels, as well as in body weight and blood pressure. Ophthalmic physical examination will focus on the risks related to the procedure (e.g. endophthalmitis and retinal detachment), and the risks related to a potential immunologic response. Imaging and functional tests will further assess any possible signs of neurotoxicity after the administration of the drug.

Because of the agonistic mode of action of BI 754132, special attention will be applied to ensure the highest level of safety for patients selecting the starting dose, the dose escalation steps and the highest dose applied (see [Section 4.1.2](#)).

Based on the safety evaluation of the SRD part of this trial, additional assessments of the optic disc, an amendment of the inclusion and exclusion criteria as well as a sentinel recruitment strategy have been implemented in the MD part.

In the trial design a sentinel approach will be used, according to EMA and ICH guidelines (EMA/CHMP/SWP/28367/07 Rev.1; EMA/CHMP/ICH/731268/1998): In the SRD part, for each cohort the first patient will be dosed and monitored to exclude acute AEs, before dosing the other patients of the same cohort. For the MD part each patient will be dosed on a sentinel approach using the 4 weeks data to decide upon the second injection of the same patient and to start the dosing of the next patient (see [Section 3.1](#)).

Moreover, the duration of observation will reflect the expected human PK of BI 754132, with a follow-up for all patients up to 100 days (i.e. the minimum observation period per patient is 100 days), with appropriate ophthalmologic and systemic evaluations (see [Section 3.1](#)). The implications of the current Coronavirus pandemic (COVID-19) are summarized in [Section 10.5](#).

Pre-clinical data show that BI 754132 can improve photoreceptor functionality, which holds promise to be beneficial in GA. However, because of the limited administration of BI 754132 during phase I and the long duration of the pathology of GA, long-term benefit for the

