For the MD part, the first patient will receive one dose and will be monitored after four weeks to exclude acute AEs and especially adverse changes of the optic disc. Data will be assessed by the dosing investigator and 2 representatives of the sponsor who are involved in the trial. The decision to continue will be based on pre-specified criteria and include certified gradings from the Central Reading Center (CRC). If no AEs or adverse changes of the optic disc are observed, the first patient can receive the second dose. The second patient can be dosed at least 7 days thereafter. The second to sixth patients will follow the same procedure as the first patient, with a safety review after 4 weeks. In addition, this safety review will include safety data from visit 4 of the previous patient (assessment 4 weeks after second injection) as well as all available safety data of the previous patients. Written minutes of this review are being distributed to all investigators participating in this trial part.

In all patients included in the MD part of the trial, safety and pharmacokinetics will be studied to 98 days after the last injection.

[figure not shown]

Figure 3.1: 2 Schematic representation of the sentinel dosing in the MD part

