#### Visual Acuity measured by ETDRS letter charts

BCVA will be determined by using the ETDRS VA chart starting at a test distance of 4 meters. The BCVA score is the number of letters read correctly by the patient. The assessment will be performed by a trained person under specified conditions regarding examination room and equipment.

For the endpoints, baseline is defined as the value at Visit 2; if not measured at Visit 2 then baseline is the value at Visit 1.

Centrally collected ophthalmological data (CFP, FAF, SD-OCT/OCT-A) will be transferred from the CRC to the sponsor's database. The local measurement data will remain at the study sites as source documents. If clinically significant worsening is observed in the safety assessments during the study, it will be reported as AE in the eCRF (please also refer to [Section 5.2.8](#)).

In the MD part, special attention should be payed to relevant adverse changes of optic disc morphology (e.g. new swelling or hemorrhage, change of cup-to-disc ratio, relevant changes of thickness of the peripapillary retinal nerve fibre layer as assessed by a circular OCT scan) or function (e.g. loss of BCVA or impaired vision). Relevant changes should be reported immediately to the Sponsor.

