#### 5.2.8.2.2 AE reporting to the sponsor and timelines

The investigator must report SAEs, AESIs, and non-serious AEs which are relevant for the reported SAE or AESI, on the BI SAE form immediately (within 24 hours) to the sponsor's unique entry point (country specific reporting process contact details will be provided in the ISF). The same timeline applies if follow-up information becomes available. In specific occasions, the investigator could inform the sponsor upfront via telephone. This does not replace the requirement to complete and send the BI SAE form.

With receipt of any further information to these events, a follow-up SAE form has to be provided. For follow-up information the same rules and timeline apply as for initial information. All (S)AEs, including those persisting after individual patient's end of trial must be followed up until they have resolved, have been assessed as "chronic" or "stable", or no further information can be obtained.

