**6.2.2.3 Follow-up period and trial completion of MD part**

Patients must continue to be followed according to the visit schedule (unless they withdraw consent for further follow-up) in order to collect data up to the end of the planned observation period. Unscheduled visits will be possible at the discretion of the investigator at any time for safety reason. The unscheduled visits may include any assessments considered necessary by the investigator. All unscheduled visits should be described and documented in the medical/source record. The investigator may decide to administer standard treatment for ocular inflammation during the follow-up period as deemed medically appropriate.

Visit 7/End of Trial:

The Visit 7/EOT will be performed 42 days after the Visit 6 (see [Flow Chart II](#)).

The Visit 7/EOT is the final visit and the trial completion page in the eCRF has to be entered.

Withdrawal of consent

If a patient is not willing to continue in the trial and wants to withdraw consent prior to the end of the trial, the investigator should offer the possibility to continue the trial without further treatment until Visit7/EOT. If patient disagrees to continue under these circumstances, Visit 6 should be scheduled as soon as possible, and also Visit 7/EOT should be performed to assess for safety.

If patient refuses to participate at a Visit 6 or Visit 7, the trial completion page of the eCRF has to be filled in.

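### In the visible protocol text, the MD-part AION/optic-disc stopping rule halts entry but does not automatically hold a third injection pending in another patient

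*Protocol*

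**What the plan says.** Protocol 3.3.4.3 sets the stopping rule: "For the following scenario further enrolment and entering into the trial will be interrupted by the sponsor once the sponsor becomes aware". The trigger specific to the multiple-dosing part is: "For the MD part: Occurrence of AION or relevant predisposing changes of the optic disc in the study eye after administration of BI 754132". It carries the same action as the general trigger above it and, unlike that one, needs no confirmation of causality. Outside the rule, the same section lets the sponsor discontinue the trial or a site.

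Dosing inside the MD part is controlled by a sentinel review. Section 1.4.3 describes it as "using the 4 weeks data to decide upon the second injection of the same patient and to start the dosing of the next patient". Section 3.1 gives the permission that follows from it: "If no AEs or adverse changes of the optic disc are observed, the first patient can receive the second dose". It then sets the stagger: "The second patient can be dosed at least 7 days thereafter". Patients two to six follow the same procedure. Their week-4 review also takes in the previous patient's Visit 4 data and whatever safety data exist on earlier patients.

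Injections fall on Days 1, 29 and 57 (Table 4.1.4: 2). On optic-disc findings, 5.2.4 says: "Relevant changes should be reported immediately to the Sponsor". No dosing consequence is attached to that report.

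**The concern.** In a single-dose part, entering a patient and dosing that patient are almost the same act, so stopping entry stops exposure. In the MD part a patient can be entered, dosed twice and waiting for a third injection when the trigger occurs in another patient. The written action protects people who have not yet entered and does not mention the one who is waiting.

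The MD safeguards were added after the single-rising-dose part. Section 1.2 reports optic ischaemic neuropathies there: a causal link could not be fully excluded, the second serious event was reported as a SUSAR, and the second AION case had not recovered. At stake is whether a twice-exposed patient could receive a further dose before a new case has been reviewed.

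**Working it through.** **Step 1: which visible rule holds which injection.**

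| Rule | Where | Mandatory effect |
|---|---|---|
| AION/disc trigger | 3.3.4.3 | Interrupts enrolment and entering |
| Week-4 sentinel review | 1.4.3, 3.1 | Gates the same patient's second injection and the next patient's start |
| Pre-injection eye examination at Visit 4 | Flow Chart II, 6.2.2.2 | Checks the waiting patient's own eye |
| Immediate report of disc changes | 5.2.4 | Informs the sponsor |
| Withdrawal for an adverse event | 3.3.4.1 | Investigator's judgement on the individual patient |
| SMC | 8.7 | General safety duty; details in the charter |

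The MD measures listed in 1.4.2.6 and 1.4.3 include no dosing hold. None of these rows automatically holds a third injection because of another patient's event.

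**Step 2: can the situation arise on the planned calendar?** Inputs, as days after a patient's own first dose (Flow Chart II): injections at 0, 28 and 56; Visits 5, 6 and 7 at 84, 112 and 154. Check against the plan: Day 155 − Day 57 = 98 days, which agrees with the follow-up after the last injection stated in 3.1.

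- Minimum stagger S between first doses, reading the 7 days as running from the previous patient's second dose and applying to every patient: 28 + 7 = 35 days.
- Interval with patient k's third injection pending: 28 to 56, so 28 days. With ±3 days on Visits 3 and 4: shortest 53 − 31 = 22, longest 59 − 25 = 34.
- Overlap between patients: at S = 35 the nominal intervals are 28–56, 63–91, 98–126, 133–161, 168–196 and 203–231. None overlap, so at most one third injection is pending at a time.

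**Step 3: event found in an earlier patient.** On patient k's clock, patient k−j's visit at offset v falls at v − jS. The table lists those strictly between 28 and 56.

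| S (days) | Scheduled visits inside the interval | Nominal days before k's third injection |
|---|---|---|
| 35 | k−1 Visit 5: 84 − 35 = 49 | 7 |
| 35 | k−2 Visit 6: 112 − 70 = 42 | 14 |
| 35 | k−3 Visit 7: 154 − 105 = 49 | 7 |
| 42 | k−1 Visit 5: 84 − 42 = 42 | 14 |
| 49 | k−1 Visit 5: 84 − 49 = 35 | 21 |
| 56 | k−2 Visit 7: 154 − 112 = 42 | 14 |
| 63 | k−1 Visit 6: 112 − 63 = 49 | 7 |
| 70 | k−1 Visit 6: 112 − 70 = 42 | 14 |
| 84 | none (k−1 Visit 6 falls on 28) | – |

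These are nominal days. Visits 5 to 7 carry ±7-day windows, so at S = 35 the k−1 Visit 5 can fall 0 to 14 days before the nominal third injection. At S = 84 a late k−1 Visit 6 (28 ± 7) can fall inside the interval.

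**Step 4: event found in the next patient.** Patient k+1 is exposed while k's third injection is pending for max(0, 56 − S) days: 21, 14, 7 and 0 at S = 35, 42, 49 and 56. Patient k+1's first scheduled post-dose visit is at S + 28, which is 63 at S = 35, 7 days after k's third injection. This route therefore depends on symptoms or an unscheduled visit, which 6.2.2.3 allows: "Unscheduled visits will be possible at the discretion of the investigator at any time for safety reason".

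**The case against.** The strongest objection is that the most likely places for a dosing hold cannot be seen. Section 1.4.2.5 is described in 11.5 as covering recommended MD safety measures; Figure 3.1: 2 shows the sentinel dosing; the pre-specified continuation criteria and the SMC charter lie outside the documents. This stands, and it limits the point to the visible text. A reader might infer that the plan has no dosing hold anywhere; the documents do not support that.

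A reader might also infer that nothing could stop the third injection. That is wrong too. Disc changes go to the sponsor at once and serious events within 24 hours (5.2.8.2.2). Urgent safety measures (8), a temporary halt or Health Authority suspension (8.6), and sponsor discontinuation are all available. The SMC has a duty to protect patients in both parts, and the patient may refuse. For harm to follow, a known event would have to be reported and the injection still be allowed. What is missing from the visible text is only the automatic step.

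A third tempting reading is that the second injection is equally exposed. It is not: its review must consider available data from earlier patients.

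It could be argued that the word entering was meant to include further doses. SAP 6.3 points the other way, since its entered set counts patients whether or not they were treated.

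Finally, case-by-case judgement in a staggered six-patient cohort is a defensible choice. But a stopping rule exists so that the first response does not rest on judgement, and this trigger already dispenses with a causality decision.

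**Conclusion.** The point holds for the visible text, with moderate confidence, and should be fixed. Followed as written, the rule would let a twice-dosed patient receive a third injection after another patient's AION is known, unless someone chose to intervene.

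The size is small: nominally one patient and one injection at a time, over about 28 days. Other patients' scheduled disc examinations fall inside that interval at nominal staggers of 35, 42, 49, 56, 63 and 70 days. These are intervals in which the gap is open. They are not event probabilities, and the documents give no basis for computing one for this population.

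The conclusion assumes the reading of the 7-day stagger stated above and that no unseen text contains a hold. If one does, the remaining issue is only that 3.3.4.3 should state it.

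**What to change.** Add one sentence to 3.3.4.3 by amendment: when the MD trigger occurs, all further BI 754132 injections in patients already entered are suspended until the SMC has reviewed the event. If such a hold already exists in the SMC charter or the continuation criteria, repeat it there so that the rule is complete in one place.

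A formal review before every Visit 4 injection would also work but is not needed to close this gap. The proposed sentence adds no review unless the trigger occurs. If it does occur, the price is a possibly delayed or lost third dose in the waiting patient, with the PK data that depend on it.

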##### Hepatic injury

A hepatic injury is defined by the following alterations of hepatic laboratory parameters:

- an elevation of AST (Aspartate Aminotransferase) and/or ALT (Alanine Aminotransferase)  $\geq 3$  fold ULN combined with an elevation of total bilirubin  $\geq 2$  fold ULN measured in the same blood draw sample, or
- aminotransferase (ALT, and/or AST) elevations  $\geq 10$  fold ULN.

These lab findings constitute a hepatic injury alert and the patients showing these lab abnormalities need to be followed up according to the “DILI checklist” provided in the ISF.

In case of clinical symptoms of hepatic injury (icterus, unexplained encephalopathy, unexplained coagulopathy, right upper quadrant abdominal pain, etc.) without lab results (ALT, AST, total bilirubin) available, the investigator should make sure these parameters are analysed, if necessary in an unscheduled blood test. Should the results meet the criteria of hepatic injury alert, the procedures described in the DILI checklist should be followed.

All AEs meeting the criteria for a dose limiting event (DLE) as defined in [Section 5.2.1](#) are defined as AESIs for this trial.

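### Severe, drug-related, non-serious reactions that are not AESIs count towards the enrolment-interruption rule (Protocol 3.3.4.3) but have no timed report to the sponsor (5.2.8.2.2)

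*Protocol*

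**What the plan says.** **The rule.** Protocol 3.3.4.3 states that "further enrolment and entering into the trial will be interrupted by the sponsor once the sponsor becomes aware" of a listed scenario. One limb is "two severe adverse reactions in two different patients (regardless of the system organ class"), where investigator and sponsor must both confirm a causal relation to the drug. The others are a single serious adverse reaction and, for the MD part, AION or relevant predisposing optic disc changes in the study eye.

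**Reporting.** Protocol 5.2.8.2.2: "The investigator must report SAEs, AESIs, and non-serious AEs which are relevant for the reported SAE or AESI", within 24 hours on the SAE form. AESIs (5.2.8.1.4) are hepatic injury and DLEs: "All AEs meeting the criteria for a dose limiting event (DLE") are AESIs for this trial. Under 5.2.8.2.1 every AE is documented on the CRF; no entry deadline is given.

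**Severity.** Intensity is graded in 5.2.8.1.5, separately from the seriousness criteria in 5.2.8.1.2.

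**MD sequence.** Under Protocol 3.1, the dosing investigator and two sponsor representatives assess each patient's four-week data before the second dose. From the second patient on, the review also takes in the previous patient's Visit 4 data and "all available safety data of the previous patients". The next patient may be dosed no sooner than 7 days after the previous patient's second dose.

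**The concern.** The severe-reaction limb is a count across patients in a multi-centre trial. A site that sees only its own patient cannot make that count, and causality must also be confirmed by the sponsor, who cannot start until told. The limb is therefore only as quick as the flow of severe reactions to the sponsor, yet the 24-hour list is built on seriousness and special interest, not on intensity. If a qualifying second reaction is waiting for CRF entry or the next review, a further patient can be enrolled and injected when the rule was meant to hold enrolment. This is a first-in-human trial in which, according to Protocol 1.2, a causal role of the drug in the optic ischaemic neuropathies could not be fully excluded.

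**Working it through.** The plan gives no figure to reproduce. The check sets the texts side by side and counts days.

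**1. Each trigger against its route to the sponsor**

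| Trigger in 3.3.4.3 | Timed route |
|---|---|
| One serious adverse reaction | Yes: 24 hours (5.2.8.2.2) |
| AION or predisposing disc changes (MD) | Yes: relevant changes of optic disc morphology or function go to the sponsor immediately (5.2.4) |
| Two severe reactions in two patients | Only if the event is also an SAE, an AESI, relevant to one, or covered by another immediate-reporting clause |

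**2. What is left uncovered**

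Start with all severe, drug-related AEs and remove:

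- those that are serious, including important medical events and the Always Serious list (5.2.8.1.2, 5.2.8.1.3);
- DLEs (5.2.1). The systemic list is paraesthesia, taste disorders, hyposmia, diarrhoea and cough. Vitreous inflammation needs grade 3+ for at least 5 days, and IOP must stay above 30 mmHg for 3 days;
- hepatic injury (5.2.8.1.4);
- in the MD part, optic disc or visual-function changes (5.2.4);
- findings on weight, blood pressure, pulse, the listed laboratory tests and ECG, which 1.4.2.6 wants reported immediately.

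The remainder is small but not empty. Examples are a severe, related, non-serious headache, or severe intraocular inflammation below the DLE grade or duration that does not affect vision. These events count under 3.3.4.3 and have only the CRF and scheduled reviews.

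**3. The MD calendar**

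Inputs: injections at 4-week intervals and visit days from Flow Chart II; the 7-day minimum from 3.1. At nominal days and the shortest spacing:

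- Patient 1: first dose day 1; review and second dose 1 + 28 = day 29; third dose 29 + 28 = day 57; next visit 57 + 28 = day 85.
- Patient 2: first dose no earlier than 29 + 7 = day 36; review and second dose 36 + 28 = day 64; next visit 64 + 28 = day 92.
- Patient 3: first dose no earlier than 64 + 7 = day 71; own review 71 + 28 = day 99.

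No review is specified between day 64 and day 71. Suppose patient 2 has an uncovered severe reaction on days 65 to 70, and patient 1 either had one already or has a late one after the day 57 injection. Two patients have now reacted, subject to confirmed causality. Neither has a scheduled visit before day 71, even with the windows: patient 1's visit is day 85 - 7 = 78 at the earliest, and patient 2's is day 92 - 3 = 89. No timed report is required before patient 3 is injected.

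**4. How often this can arise**

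Six MD patients give five gaps. On MD events alone, two patients must already have been dosed, so four gaps are exposed (before patients 3, 4, 5 and 6, assuming no replacements). Each gap admits one new patient before the next specified review.

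**The case against.** **Routes exist.** A reader might infer that these reactions have no reporting route. The documents do not support that. All AEs go on the CRF, and SAP section 3 shows that data are entered in an EDC system. In the SRD part, two sponsor representatives review each cohort's first patient (3.1), and the SMC considers AEs that are not DLEs before the next cohort (4.1.4). In the MD part, sponsor representatives review every patient, and 7.2.7 says the sponsor monitors safety continuously. This stands. What is missing is a timed report, not a route: none of these provisions says when a severe non-serious reaction must be notified.

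**The MD review is stricter than the trigger.** Under 3.1 the second dose follows if no AEs or adverse disc changes are seen, and under 1.4.3 the same four-week data decide whether the next patient starts. A single AE found at review is already a point for assessment. This also stands, and it covers what happens before the review. It does not cover the days between the review and the next first dose, or late events in earlier patients.

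**The delay is easily overstated.** Successive reviews are 64 - 29 = 35 days apart at the shortest nominal spacing, and a reader might take this as a five-week delay in awareness. It is only the distance between reviews. Nothing in the documents says the sponsor sees no CRF entry or site contact in between, and the specified interval before the next first dose is at least 7 days. One severe reaction also does not meet a two-patient trigger.

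**Unseen documents may help.** The CRF guidance, ISF and SMC charter may set a deadline. This is a fair limit on the finding, but the protocol points to none of them for this trigger.

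**Conclusion.** The mismatch between 3.3.4.3 and 5.2.8.2.2 is real and narrow. The severe-reaction limb is the only trigger with events that have no timed report. The live exposure is in the MD part, because Protocol 1.2 says the SRD patients had completed. It consists of the gap of at least 7 days after each review, plus late events in earlier patients, with one new patient per gap.

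The conclusion assumes that some severe, related reactions are neither serious nor AESIs. None is described so far: Protocol 1.2 reports all ocular AEs other than the optic ischaemic neuropathies as mild, and all systemic AEs as mild or moderate and unrelated to the drug. It also assumes that no unseen document sets a deadline.

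A reader might go further and conclude that the rule cannot work promptly. The documents do not show that. Prompt CRF entry or a telephone call would let it work; the protocol simply does not require either for these events.

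**What to change.** In 5.2.8.2.2, add to the events reported within 24 hours: *any AE of severe intensity that the investigator judges related to trial drug*. Every reaction that the severe limb counts would then reach the sponsor on the SAE timeline, and the two sections would agree. The trigger, the doses and the visit schedule are unchanged.

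The cost is one line in the protocol, the same line in the site reporting instructions, and a few extra 24-hour forms. The SRD intensity data suggest these would be rare. The line shortens only the time from site awareness to sponsor awareness; it does not help with an event that the patient has not yet told the site about. If the CRF guidance or SMC charter already sets an equivalent deadline, a cross-reference in 3.3.4.3 would be enough.
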